4.2 Drug/Device Handling: N/A

4.3 Biosafety: N/A

4.4 Stem Cells: N/A

5.0 Procedures Involved

5.1 Study Design: The study design is cross-sectional. 150 target children (10- to 15-year-olds) will be randomly assigned to one of three conditions: (1) no social support (standard MRI scanning condition); (2) presence of a parent; or (3) presence of a close friend. Outcome measures will be compared across the three social buffering conditions. Pubertal stage will be included as a continuous variable in analyses of physiological and/or brain responses.

Two tasks will be used during the MRI scanning. Both have been shown to activate stress-related regions of the brain in past studies and have been used by our labs. The order of these two tasks will be counterbalanced.

Based on the results of piloting social buffering will EITHER be done with the presence of a buffer in person, or, displayed on screen via a live Zoom feed. All conditions will use the same modality.

Study Overview:

Visit 1: Parent and child will participate in an online video session (via Zoom) lasting approximately 2 hours. Following a detailed overview of study and consent/assent procedures, participants will be asked to complete the following measures:

Parent:

- Questionnaire regarding family income, education level, and family composition
- Parent-report questionnaire about child's general health, behavior, and development (MacArthur Health Behavior Questionnaire; HBQ)
- Parent-report MRI safety screening questionnaire about the child to rule out any contraindications for MRI scanning
- *[If the child is randomized to the parent-present buffering condition],* self-report MRI safety screening questionnaire to rule out any contraindications for sitting in the MRI area

PROTOCOL TITLE: An MRI Study of Learning and Social Support

VERSION DATE: v.10 2024.12.18

- Child life challenges question

Children/adolescents:

- Questionnaire about general health, behavior, and development (MacArthur Health Behavior Questionnaire; HBQ)
- Questionnaire about their relationships with their parents and their best friend (Network of Relationships Questionnaire)
- Questionnaire about anxiety in different contexts (State-Trait Anxiety Inventory for Children)
- Pubertal development questionnaire (Morris and Udry, 1980)
- Safety screening questionnaire to confirm safety in the MRI scanner
- Perceived stress questionnaire
- Child life challenges questionnaire

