- Completion of the Network of Relationships questionnaire
- Sit next to scanner bed and listen to music, radio, audio book, podcast, etc. or read a book for duration of MRI scan (approx. 1 hour) OR join the session online via video conference call to research staff in the MRI console room for duration of MRI scan , chatting with the first child periodically.
- *Note: Friend's parent will complete a full consent procedure over the telephone or video conference call prior to the session and will return a signed consent and child safety-screening form via REDCap or by mail or with the participating family.*

5.2 Study Procedures:

Social Buffering Manipulations: Will include 3 between-subjects conditions and both sexes. Participants will be randomly assigned to No Social Partner, Parent, or Close Friend conditions. Definition of Close Friend. We will ask the parent to have the child select the close same-sex friend they want to have accompany them. The parent then has to contact that child's family and get their permission for us to contact them. We have successfully conducted studies in which the child brings their best friend.

Affective Paradigms: Aversive Learning Paradigms: Consent, assent, and questionnaires will occur during an online session (to reduce in-person requirements; minimize the impact of COVID on study feasibility.) At the session, after a reminder of procedures, youth will be separated from their parents. Youth will be taken to a private changing room to change into

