
Pubertal Development: We will create a summary pubertal development index from parent & child report. A planned nurse exam was dropped due

to COVID and funding considerations. Parents & youth will complete the Morris and Udry (1980) pubertal development questionnaire, which allows placement in Tanner stages for hair, testicles, and breast development.

Questionnaires.

Demographic Questionnaire: Parents will complete information on pre-tax family income, education level of parent(s), composition of the household, and medications that the child regularly takes.

Daily Diary: The parent and the youth both will report the following for the child that day: the time of wake up, medication usage, illness/fever, physical activity, and caffeine consumption.

Relationship Quality: Youth and their friend (when assigned to friend buffer condition) will complete the Network of Relationships Inventory (NRI, Furman & Buhrmester, 2009) for parents and their close friend. This questionnaire is based on an integration of attachment and Sullivanian theory and assesses three systems that are expected to be key in close relationships: attachment, caregiving and affiliation. The scales are: companionship, seek safe haven, seek secure base, provide safe haven, provide secure base, conflict, antagonism and criticism. We will also include the full set of scales from the NRI,: Each scale consists of 3 items scored on a 5-point Likert scale. Psychometric qualities are high. Condition differences in quality of relationships will be examined and included as covariates if groups differ significantly. Otherwise, in follow-up analyses we will examine whether social buffering effects are stronger in relationships the child views as more supportive.

MacArthur Health and Behavior Questionnaire (HBQ) for 9-18 Year-Olds (Parent and Child, 2.1): This questionnaire was developed by Marilyn Essex based on the original HBQ for 4-8 year olds. We have used it many times. The scales we proposed to use here have high reliabilities (Cronbach alpha's > .8). We will use the peer scales (acceptance/rejection, bullied, relational victimization, asocial, behavioral inhibition) and broad-band symptoms scales (Internalizing, Externalizing). These measures will be examined for balance across groups and if differences by condition, pubertal stage, or sex are found, will be entered as covariates.

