15.0 Statistical Considerations

15.1 Data Analysis Plan:

Preliminary Analyses to Determine Covariates Needed for Primary Analyses.

The purpose of collecting data on potential covariates is to identify variables

that are correlated with both the independent variable (social buffering condition, sex, pubertal stage) and the primary outcome measures. Those covariates that are associated with the independent and outcome variables will be controlled for in the primary analyses. Those that are not will be used to describe the sample, but will not need to be included in the analyses to obtain unbiased estimates. For each potential covariate, we will conduct correlations or t-tests with pubertal stage, and t-tests, ANOVAs, or chi-square tests (as appropriate) with sex and condition. If data do not confirm to modeling assumptions, we will use nonparametric analogs instead.

Preliminary Analyses of Imaging Data to Yield Primary Outcome Measures: fMRI data will be analyzed in FSL software (version 6.0.1) to generate voxel-wise contrast maps. Mean signal values will be extracted from these maps in a priori regions of interest for every participant using the methods described below. These preliminary analyses are used to generate the fMRI outcome variables of interest. The values of these outcome variables for each participant will be used in the general statistical analyses described in the next section. In total, these preliminary analyses will yield 6 primary task-related outcome variables, and 6 primary connectivity-related outcome variables.

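### A Visit 1 parent form issued only in the parent condition can reveal the assignment before questionnaires that may become covariates are completed, and the covariate rule would then adjust for any resulting shift

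*Combined protocol and SAP*

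**What the plan says.** Section 5.1 describes the first session: "Visit 1: Parent and child will participate in an online video session (via Zoom) lasting approximately 2 hours". The parent's list includes a self-report screen for sitting in the MRI area, given "If the child is randomized to the parent-present buffering condition". The same list includes the parent HBQ. The child's list for that session includes "Questionnaire about their relationships with their parents and their best friend", the child HBQ, and anxiety and perceived-stress scales. The parent-arm self-screen is listed again at Visit 2.

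Three rules govern use of these scores:

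- Relationship quality (Section 5.2): "Condition differences in quality of relationships will be examined and included as covariates if groups differ significantly". Otherwise it is used in a follow-up of whether buffering is stronger in relationships the child sees as more supportive.
- HBQ (Section 5.2): "if differences by condition, pubertal stage, or sex are found, will be entered as covariates".
- All potential covariates (Section 15.1): "Those covariates that are associated with the independent and outcome variables will be controlled for in the primary analyses". Condition is one of the independent variables named there.

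For the friend arm, Section 5.2 says "We will ask the parent to have the child select the close same-sex friend they want to have accompany them", without placing this step before or after Visit 1. The only masking-type statement is in Section 6.1 and concerns biospecimen labels.

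**The concern.** A baseline covariate should be measured before assignment can influence it. If these ratings were completed before anyone in the family could know the arm, a difference between conditions could arise only by chance, and adjusting for it would do no harm. Once the arm can be known, a difference may also be a consequence of assignment: a child about to be accompanied by a parent may describe that relationship differently, and a parent may answer the HBQ differently. The rule in Section 5.2 then tends to pick out the trials in which this has happened. It treats an effect of assignment as a confounder, so the primary condition contrast can lose part of a real effect or gain a spurious one.

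**Working it through.** **What the text establishes.** An arm-specific parent form at Visit 1 requires the arm to be known to staff by then. A parent who has heard the study overview and receives that form can infer the parent condition; one who does not receive it can infer the reverse. The relationship ratings come from the child, on a separate list, and the lists are not a stated sequence. So the route to the parent is in the text; the route to the child is possible only.

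**Size.** The documents give no figure on this point, so there is none to reproduce. What follows is an illustration. Inputs from the documents: 150 children in three conditions (Section 5.1) and 50 bringing friends (Section 10.1), taken as 50 per arm. Assumed inputs: a reporting shift d of 0.2 to 0.4 SD in one arm, and a slope b of 0.3 between true relationship quality and outcome (both SD 1).

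1. Let Q be true quality, S = Q + dT the reported score (T = 1 in the shifted arm), and Y = τT + bQ + e the outcome. Substituting Q = S − dT gives Y = (τ − bd)T + bS + e. Adjusting for S therefore estimates τ − bd, a bias of −bd.
2. The check for group differences is taken as a one-way ANOVA at .05 on 2 and 147 df. With one arm shifted, the noncentrality is 50 × d² × 2/3 = 33.33 d².
3. The rule (adjust if the ANOVA is significant, otherwise do not) was simulated with no true condition effect, 40,000 trials per row.

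| Shift d | Noncentrality | Rule fires | Bias when it fires (b × d) | Mean bias, all trials | Type I error |
|---|---|---|---|---|---|
| 0 | 0 | 5% | 0 | 0.00 | 5% |
| 0.2 | 1.33 | 16% | 0.06 | 0.02 | 5% |
| 0.3 | 3.00 | 32% | 0.09 | 0.05 | 6% |
| 0.4 | 5.33 | 52% | 0.12 | 0.08 | 7% |

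Biases are shown as magnitudes in outcome SD. The overall mean exceeds firing rate × bias (0.16 × 0.06 = 0.01 in the second row) because trials in which the rule stays silent tend to be those where true quality happened to be low in the shifted arm. The unadjusted estimate in those trials errs slightly in the same direction. For scale, the standard error of an unadjusted two-arm contrast is √(2/50) = 0.20 SD.

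4. Section 15.1 also asks for association with the outcome. Adding that requirement (p < .05, same slope) lowers the firing rates only to about 15, 31 and 50%; the mean bias stays at about 0.02, 0.05 and 0.08 SD.
5. Direction: if better-rated relationships go with a smaller stress response and knowing the arm raises the rating, adjustment removes part of a buffering effect. If either sign is reversed, it adds to one. The documents fix neither sign.

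**The case against.** The strongest reply is that disclosure is inferred. The form goes to the parent, while the child gives the relationship ratings; the form could be given last; and nothing says the child is told. That stands. A reader might infer that families do know the arm while answering, but the documents support only that they can.

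The textual cue also concerns the parent arm. The friend's own forms are listed at Visit 2, and when the friend is chosen is not stated. A reader might infer the same disclosure in the friend arm; the text does not show it. The arithmetic applies to whichever single arm is shifted.

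If buffering is by video, the parent sits in a separate room and an MRI-area screen may be unnecessary. That is possible, but Section 5.1 makes the form depend on arm alone.

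A reader might further infer that the follow-up on more supportive relationships is ruined. This does not follow. A constant shift leaves the within-arm slopes unchanged (simulated bias in the slope difference about 0.00), and Section 5.2 runs that follow-up only when groups do not differ significantly. Harm there would need a shift that varies with relationship quality, for which the documents give no basis.

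Nor are all Visit 1 scales equally exposed. Perceived stress covers the past month and Child Life Challenges covers lifetime adversity, so knowledge of the arm is less likely to move them.

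Finally, shift and slope are assumptions, and the bias averaged over all trials is small against a standard error of 0.20 SD. That also stands, and limits the point to a minor one.

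**Conclusion.** The point holds in a limited form. A stated step at Visit 1 can reveal the assignment to the parent in the session where potential covariates are collected. Nothing in the plan prevents this, and stated rules would adjust for any shift that results. Whether a shift occurs, in whom, and in which direction cannot be known from the documents. Under a shift of 0.2 to 0.4 SD in one arm and a slope of 0.3, the consequence is modest: 0.06 to 0.12 SD when adjustment is triggered, 0.02 to 0.08 SD on average, and type I error of about 5 to 7%. It is worth correcting because the correction is cheap, not because the trial's conclusions are shown to be at risk.

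**What to change.** For families not yet enrolled: state when the assignment is generated and when it is disclosed, and reveal it only after the Visit 1 questionnaires are submitted. Give the MRI-area self-screen to every parent at Visit 1, so that receiving it says nothing about the arm. Alternatively, if those responsible for MRI safety find it sufficient, keep only the Visit 2 screen that Section 5.1 already lists.

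For all participants: do not select relationship quality or the HBQ as covariates by a test for condition differences, and report the condition contrast without them. This part matters because reordering forms cannot help children already tested; Section 20.1 refers to participants who had completed the study by early 2024, and this protocol version is dated December 2024.

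Cost: one short form for all parents, a change in the order of Visit 1, and a few sentences in Sections 5.2 and 15.1. Contact with the friend's family and their consent could start only after Visit 1, and Visit 1 would differ slightly between earlier and later participants. If disclosure already follows the questionnaires in practice, stating so settles the timing question. Label: cheap improvement.

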3.0 Study Endpoints/Events/Outcomes

3.1 Primary Endpoint/Event/Outcome:

Neural activity in vmPFC, insula, amygdala, and hypothalamus; salivary cortisol, heart rate, respiration, skin conductance

3.2 Secondary Endpoint(s)/Event(s)/Outcome(s):

Exploration of possible sex differences in across buffering conditions later in puberty but not earlier in puberty.

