Hair Hormones: Hair will be assayed for a full panel of stress, puberty, and sleep hormones. Hair cortisol provides a measure of the stress sensitive hormone cortisol indexed over approximately 3 months. We will take the ~ 3 cm of hair next to the scalp on the posterior vertex. Based on an average hair growth rate of 1 cm/month, this represents hair grown over the 3-month period prior to sampling. Wash and steroid extraction procedures will be conducted in [name]'s ISO lab, following their published protocol (Stalder & [name], 2012, study II) with 7.5 mg of hair used for analysis. Participants will also complete a questionnaire about hair products and treatment that can be included as covariates. We anticipate that we will not be able to collect hair cortisol for some participants whose hair is too short or who refuse this sampling. In previous work, we have

had missing samples for ~ 10% of participants. We will deal with this using multiple imputation by chained equations (MICE) to impute missing data.

Physiological Recording: Participants will wear a combination of standard Siemens physiological recording equipment for the MRI environment (respiration belt, pulse oximeter, EKG leads). In addition, they will wear BioPac MRI-safe skin conductance electrodes. Samples will be collected throughout the entire MRI scan. Response measures will be computed by regressing aversive learning condition values on comparison values during the resting state scan and saving the residual as the response measure. If the parent and child opt-in, the child will wear an actigraphy device for several days. The actigraphy device uses accelerometers and gyroscopes to measure body movement. After completion of actigraphy data collection, the parent will return the device back to the researchers.

All questionnaires and surveys are included in the ETHOS portal. Contact information and child age will be obtained from an existing registry of families who have expressed interest in child development research (specifically, parent name(s), address, phone number, email address, child name, child sex, and child birthdate). All other data will be acquired directly from the participants, and information obtained from the participant registry will be verified verbally with the parent. Birthdate will be collected from parent at the session so that a precise age of child can be obtained.

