The primary analyses will consist of a series of multiple regression models. For each dependent variable, variation in neural activity, cortisol, and physiological responses, we will begin by testing the three-way interaction between social buffering condition, sex, and pubertal stage for all outcomes. If the three-way interaction is not significant, we will then examine all two-way interactions. If the two-way interactions are not significant, we will then examine main effects only models. If the three-way interaction is significant, we will not examine any other model. If condition is significant as an interaction or as a main effect, we will examine all pairwise comparisons using Tukey's Honestly Significant Difference test.

Multiplicity of testing. We will correct for multiple comparisons using the Benjamini-Hochberg (BH) correction. The BH method works by controlling the false discovery rate, and relative to the Bonferroni's correction is more powerful, while still adequately protecting against Type I error (Williams, Jones, & Tukey, 1999).

Mediational Analysis. When changes in activity of brain regions differ by condition or condition by pubertal status and we also see condition or condition by pubertal status differences for cortisol or physiological measures, then we will examine whether brain activity differences mediate the neuroendocrine or physiological differences. This will be examined using path analysis, while controlling for covariates identified in the preliminary covariate analysis, and will be estimated using the lavaan package in R (Rosseel, 2012).

The significance of all indirect effects will be assessed using bias-corrected 95% confidence intervals (Efron & Tibshirani, 1986), where confidence intervals that are non-overlapping with zero will be considered significant.

Power Analysis for the Mediational Analysis: To assess power to detect mediation, we performed a Monte Carlo-based power analysis using simulated data. We varied the parameter values to roughly correspond to Cohen's criteria for small, medium, and large effects. This resulted in a total of 27 conditions, which we examined at our target sample size of 200. Each

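### Pre-computing heart rate, respiration and skin conductance as residuals on rest can bias their puberty and sex effects; the resting value belongs in the primary model itself

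*Combined protocol and SAP*

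**What the plan says.** Section 3.1 lists "salivary cortisol, heart rate, respiration, skin conductance" among the primary outcomes, next to the neural measures. For the recorded physiological signals, section 5.2 (Physiological Recording) sets out a first step, in which task values are regressed "on comparison values during the resting state scan and saving the residual as the response measure". No other predictor is named in that regression.

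Section 15.3 is the second step: "The primary analyses will consist of a series of multiple regression models". It begins by "testing the three-way interaction between social buffering condition, sex, and pubertal stage for all outcomes" and works downwards: "If the two-way interactions are not significant, we will then examine main effects only models". Section 5.1 adds: "Pubertal stage will be included as a continuous variable in analyses of physiological and/or brain responses".

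No section puts the resting value into the second-step model. The covariate rule in section 15.1 would not bring it in either. That rule requires association with a predictor and with the outcome, and a least-squares residual has zero sample correlation with the variable it was residualised on.

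**The concern.** When task values are regressed on rest alone, the slope for rest also absorbs the part of any puberty or sex effect that overlaps with rest. That part is removed from the residual, and the second regression cannot restore it because rest is no longer in the model. Randomisation gives no protection here: puberty and sex are observed characteristics and may well be related to resting physiology.

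At stake are the puberty and sex coefficients for three primary physiological measures. The study is framed around physiological and neural responses across the pubertal transition (section 2.3), and puberty and sex are in every primary model. A distorted coefficient costs power or, when both are related to rest, can attribute an effect to the wrong predictor.

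**Working it through.** **The plan's own figure.** The documents give no figure for the residual step. The only figure for the primary regression is the minimum detectable f² in section 15.2. With 2 numerator and 176 denominator degrees of freedom (n = 200, 23 predictors) I obtain 0.0548 against the stated 0.056; at n = 160, 0.0709 against 0.070. It reproduces to within about 2%, and the present point does not depend on it.

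**Inputs.** From the documents: the two-step construction (5.2, 15.3) and 150 analysed participants (10.1). Assumed, because the documents are silent: the correlation r of rest with puberty or sex, a rest-to-task slope b = 0.7, and the effect sizes and error SDs below.

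**One rest-related predictor.** Let task Y = bR + gX + e, with R and X of unit variance and corr(X, R) = r.
- Step-1 slope = b + g·r.
- Residual = gX - (g·r)R + e.
- Regressing this on X alone gives g - g·r·r = g(1 - r²).
- Regressing Y on X and R together gives g.

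| Size of r | Share kept | True 0.300: two-step, simulated | Rest in model, simulated |
|---|---|---|---|
| .1 | 0.99 | 0.295 | 0.300 |
| .3 | 0.91 | 0.271 | 0.300 |
| .5 | 0.75 | 0.225 | 0.301 |

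(n = 150, 4,000 replicates.) For sex, a true effect of 0.500 with a correlation of size .3 gives 0.500 × 0.91 = 0.455 by formula and 0.454 by simulation, against 0.501 with rest in the model.

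**Power.** For a true puberty effect of 0.20, n = 150, two-sided 5% level, 6,000 replicates, two-step against rest in the model:
- Error SD 0.71: 0.92 v 0.92 (r = .1), 0.88 v 0.90 (r = .3), 0.74 v 0.83 (r = .5).
- Error SD 1.0: 0.67 v 0.67, 0.60 v 0.64, 0.43 v 0.55.

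**Two rest-related predictors.** Let R = -0.4P - 0.8S + noise, with total variance 1, P of unit variance and S coded ±0.5 (variance 0.25). The step-1 slope exceeds b by d = gP(-0.4) + 0.25·gS(-0.8), and the two-step coefficients are gP + 0.4d and gS + 0.8d.
- gP = 0, gS = 0.5: d = -0.10. Puberty becomes -0.040 (simulated -0.039) and sex 0.420 (0.417). A puberty effect appears where there is none.
- gP = 0.10, gS = -0.5: d = -0.04 + 0.10 = 0.06. Puberty becomes 0.124 (0.123), an inflation, and sex -0.452 (-0.451).

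With rest in the model, the simulated values were within 0.001 of the truth in both cases.

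**Rest measured with error.** With reliability 0.7 and a puberty slope on rest of -0.4:
- True puberty effect 0.300: 0.206 with rest in the model, 0.182 with the residual.
- True effect 0: -0.096 and -0.085.

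**Condition.** When rest does not differ by arm, condition is uncorrelated with rest apart from chance, and the argument above leaves its terms nearly unchanged. Suppose instead that the partner shifts rest by -0.4 (parent) and -0.2 (friend), with direct effects of -0.30 and -0.15. The totals are -0.30 + 0.7(-0.4) = -0.58 and -0.15 + 0.7(-0.2) = -0.29. Rest in the model gave -0.301 and -0.148; the residual gave -0.292 and -0.143.

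**The case against.** Four arguments can be made for leaving the plan alone.

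1. *The bias may be negligible.* It needs puberty or sex to be correlated with rest, and no such figure is reported. For r up to .3 the loss is at most 9% and the fall in power a few points at most. This stands.

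2. *The affected terms are not the central ones.* The hypotheses in section 2.3 concern buffering and its waning with puberty, that is, condition and condition-by-puberty. These change little unless rest differs by arm, and main-effects-only models are reached only when no interaction is significant. This also stands and limits the importance of the point.

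3. *Adjusting for rest in the model is not unbiased either.* A reader might infer that it estimates puberty and sex effects without bias. That needs linearity, an error-free rest measure and a target defined as conditional on rest. The documents specify no such target, and rest is one 5-10 minute scan. With reliability 0.7 the covariate model is biased too, slightly more than the residual when the true effect is zero. The stronger inference is not supported.

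4. *Rest is not a pre-randomisation baseline.* Under sections 5.1 and 5.2 it is recorded in the scanner after allocation, with the parent or friend present or on video throughout the scan. If the partner calms the child at rest, adjustment removes part of the buffering effect. This is correct, but the planned residual has the same limitation to almost the same degree (-0.292 against -0.301, for a total of -0.58). It is no reason to prefer the residual.

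**Conclusion.** The point holds in a limited form. The plan does use a two-step residual and leaves rest out of the primary model. If puberty or sex is correlated with rest, its rest-conditional effect on heart rate, respiration and skin conductance is then biased. With one such predictor the effect is multiplied by (1 - r²): a loss of 1%, 9% and 25% at r = .1, .3 and .5. These values of r are assumed, and the power figures also rest on the assumed effect, slope and error SD.

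A reader might infer that the method always shrinks these effects. The documents do not establish that any shrinkage will occur, and with puberty and sex both related to rest the bias can inflate an effect or create one. Nor do the documents show material damage to the condition or condition-by-puberty tests. This is a low-priority improvement, worth making because it is cheap and needs no new data.

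**What to change.** - In the section 15.3 models for heart rate, respiration and skin conductance, use the task value as the outcome and enter the resting value as a covariate in the same model, whatever the section 15.1 screening shows. Keep the residual for plots only.
- Do the same in any mediation path model that uses these outcomes.
- State that the resulting effects are conditional on rest.
- Report resting values by condition, so that readers can see whether the partner may have altered them.

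The cost is a wording change in sections 5.2 and 15.3, respecified path models and one degree of freedom; the data are the same. Two limits remain. Measurement error in the short rest scan leaves some bias in puberty and sex effects. And, as with the planned residual, adjusting for a rest value taken after randomisation with the partner present does not recover the total buffering effect if the partner changes rest.
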